10.2.2 Adverse Event Incidence

The number and percentage of subjects experiencing one or more adverse events in the following adverse event categories during the 26-week Treatment Period will be summarized for each treatment group and for overall subjects by primary SOC and PT.

- Any TEAE
- Any serious TEAE
- Any TEAE that led to discontinuation of study drug

The percentage of subjects in the LCIG group and in the OMT group will be compared using Fisher's exact test. Only P values ≤ 0.100 when rounded to three digits will be presented.

The number and percentage of subjects experiencing one or more adverse events in the following adverse event categories during the Extension/Transition Period will be summarized for OMT/LCIG subjects who enter the Extension/Transition Period by primary SOC and PT.

- Any TEAE
- Any serious TEAE
- Any TEAE that led to discontinuation of study drug

The number and percentage of subjects experiencing one or more TEAEs during the 26-week Treatment Period will also be summarized for each treatment group and for overall subjects by maximum severity category (mild, moderate, severe, or unknown) and primary SOC and PT. Subjects reporting more than one TEAE for a given PT will be counted only once for that term in the most severe category reported. If a subject has an adverse event with unknown severity, then the subject will be counted in the severity category of "unknown," even if the subject has another occurrence of the same event with a severity present. The only exception is if the subject has another occurrence of the same

adverse event with the most extreme severity – "Severe." In this case, the subject will be counted under the "Severe" category.

The number and percentage of subjects experiencing one or more TEAEs during the 26-week Treatment Period will also be summarized for each treatment group and for overall subjects by maximum relationship category (reasonable possibility, no reasonable possibility, or unknown), as assessed by the investigator, and primary SOC and PT. Subjects reporting more than one TEAE for a given PT will be counted only once for that term in the most related category reported. If a subject has an adverse event with unknown relationship, then the subject will be counted in the relationship category of "unknown," even if the subject has another occurrence of the same event with a relationship present. The only exception is if the subject has another occurrence of the same adverse event with a relationship assessment of "Reasonable Possibility." In this case, the subject will be counted under the "Reasonable Possibility" category.

The number and percentage of subjects experiencing one or more adverse events in the following adverse event categories 26-week randomized treatment period will be summarized by PT. The PTs will be presented by decreasing frequency overall.

- Any TEAE
- Any TEAE that was moderate or severe

A list of subject numbers associated with each PT will also be presented for all TEAEs.

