4.0 Study Objective

Primary Objective:

The primary objective of this study is to examine the effect of LCIG relative to that of OMT on NMS associated with advanced PD as assessed by the NMSS Total Score and the Modified PDSS-2 Total Score.

Secondary Objectives:

To assess the effect of LCIG relative to that of OMT on the motor symptoms/motor complications, safety, tolerability and health-related outcome measures.

Motor symptoms/motor complications will be measured by:

- UPDRS Parts III and IV

Safety and tolerability will be assessed by:

- Adverse event monitoring
- Neurological exams
- Clinical laboratory evaluations
- Electrocardiogram
- Vital signs and weight
- Columbia Suicide Severity Rating Scale (C-SSRS)
- Minnesota Impulsive Disorders Interview (MIDI)
- Sleep Attacks Questionnaire (SAQ)

Health Related Outcomes will be measured by:

[figure not shown]
- Parkinson's Disease Questionnaire-8 (PDQ-8)
- Clinical Global Impression of Change (CGI-C)
- UPDRS Parts I and II
- Patient Global Impression of Change (PGIC)
- Parkinson Anxiety Scale (PAS)
- Geriatric Depression Scale (GDS-15)
- King's PD Pain Scale

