4.3 Sample Size

Approximately 88 subjects will be enrolled into the study and randomized in a 1:1 ratio to either optimized medical treatment or LCIG. There are no data on NMSS or PDSS-2 available from randomized trials comparing LCIG and OMT. Interim data from ongoing Phase 3b Study M12-920 showed that the improvement in NMSS total score from baseline to Week 12 is 24.8 in the LCIG group with standard deviation of 24. Results from Zibetti et al (2013) showed that the improvement in PDSS 2 total score after an average of 3.5 months of LCIG treatment was 13.1. The standard deviation was not provided and is estimated to be 12.2 assuming the correlation between baseline and follow-up visits is 0.5.

The significance level for this study is 0.05. For sample size determination, it is assumed that the improvement in the OMT group is 33% of the LCIG group, i.e., the improvement is 8.2 on NMSS total score and 4.3 on PDSS-2 total score, and that the correlation between these 2 measures is 0.5. Simulation showed that a study with 37 subjects per

group will have 90% power to declare statistical significance on at least one of these 2 alternative primary endpoints after multiplicity adjustment using Hochberg procedure. It is further assumed that 10% of randomized subjects in either treatment group will not provide post-randomization efficacy assessment. Additional simulations showed that 44 subjects per group will provide 90% power in the sensitivity analysis using baseline observation carried forward for subjects without post-randomization assessment. Therefore the total planned enrollment is decided to be 88 subjects.

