10.0 Safety Analysis

10.1 General Considerations

Unless noted otherwise, all safety analyses will be performed on the Safety Dataset. Treatment group differences in safety parameters are evaluated using two-sided test at the significance of 0.050.

Unless otherwise specified, treatment group differences in continuous safety variables (e.g., changes from baseline to final observation on laboratory test variables) will be

assessed using an ANOVA model with the term of treatment, and the treatment group differences in binary safety variables will be evaluated using a Fisher's exact test.

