10.3.1 Analysis of Mean Changes for Laboratory Tests

Analyses of mean change from baseline to each planned visit and to the minimum, maximum and final value during the 26-week randomized treatment period will be presented by treatment group for each continuous hematology, chemistry, urinalysis, and special laboratory variable.

For each change from baseline analysis, the following summary statistics for each treatment group will be presented: sample size, baseline mean, visit mean, and the mean, standard deviation, and median of the change from baseline. The baseline and visit means will be calculated for each visit for subjects who have both a baseline and visit value. The

mean changes for the LCIG group and for the OMT group during the 26-week randomized treatment period will be compared using an ANOVA with treatment as the factor. LS mean, standard error, 95% confidence interval and *P* value will be presented.

Analyses of mean change from the Extension/Transition Period baseline to each planned visit and to the minimum, maximum and final value during the Extension/Transition Period will be presented for each continuous hematology, chemistry, urinalysis, and special laboratory variable for OMT/LCIG subjects who enter the Extension/Transition Period.

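### Adverse events are compared between arms only by Fisher's test, with P hidden above 0.100 in SAP 10.2.2 and no effect interval planned, so the tables do not show how much excess harm remains possible

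*SAP*

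**What the plan says.** Protocol 4.0 makes relative safety a secondary objective: "To assess the effect of LCIG relative to that of OMT on the motor symptoms/motor complications, safety, tolerability and health-related outcome measures".

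SAP 10.1 sets the general rule for safety comparisons: "Treatment group differences in safety parameters are evaluated using two-sided test at the significance of 0.050". It adds that "differences in binary safety variables will be evaluated using a Fisher's exact test". Protocol 8.1.4 has the same default.

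SAP 10.2.2 covers any TEAE, any serious TEAE and any TEAE leading to discontinuation. Each "will be summarized for each treatment group and for overall subjects by primary SOC and PT", as numbers and percentages. Then: "The percentage of subjects in the LCIG group and in the OMT group will be compared using Fisher's exact test". The display rule follows: "Only P values ≤ 0.100 when rounded to three digits will be presented".

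That rule is written only in SAP 10.2.2. The overview (10.2.1) and the special-interest composites (10.2.3: GI and procedure events, polyneuropathy, weight loss) do not repeat it. They fall under the Fisher default in 10.1. No section plans a risk difference, a risk ratio or an interval for an adverse event.

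Continuous safety variables are treated differently. For laboratory changes, SAP 10.3.1 states: "LS mean, standard error, 95% confidence interval and *P* value will be presented". SAP 10.4.1 (vital signs and weight) and 10.5.1 (ECG) do the same.

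**The concern.** The sample was sized on NMSS and PDSS-2 alone. At that size Fisher's test has little power for moderate differences in uncommon events, so many real excesses will give P above 0.100. The P cell is then empty, and P = 0.11 looks the same as P = 1.00.

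The counts remain visible, but counts carry no statement of uncertainty. A clinician weighing an invasive treatment against continued medical therapy needs to know how large an excess the data leave open. As planned, neither the counts nor the empty cell says so, and this affects the categorical harms that bear most directly on the secondary safety objective.

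**Working it through.** **Inputs from the documents.** SAP 4.3: "Approximately 88 subjects will be enrolled into the study and randomized in a 1:1 ratio", which is 88/2 = 44 per arm. Test, level and display threshold: SAP 10.1 and 10.2.2. LCIG event rates: Protocol 3.2, Table 1 (25 preferred terms, 10.0% to 33.3%, N = 412) and 47.1% for any serious event.

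**Assumption.** No OMT event rates are given. A true doubling is taken as the reference case and the OMT rate is varied.

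**The plan's own figure first.** Simulating the stated design (NMSS 24.8 vs 8.2, SD 24; PDSS-2 13.1 vs 4.3, SD 12.2; correlation 0.5; t-tests with Hochberg at 0.05) gives 90.4% power at 37 per group. At 44 per group, with zero change for a random 10%, it gives 90.3%. The planned size reproduces, but it says nothing about adverse events.

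**Chance that a P value is printed.** For event counts x (OMT) and y (LCIG):

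Pr(print) = Σ Bin(x; 44, p_OMT) × Bin(y; 44, p_LCIG), summed over all (x, y) whose two-sided Fisher P, rounded to three digits, is ≤ 0.100.

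This is an exact enumeration of the 45 × 45 possible tables.

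| OMT rate | LCIG rate | P printed | P cell empty |
|---|---|---|---|
| 2% | 4% | 1% | 99% |
| 5% | 10% | 11% | 89% |
| 10% | 20% | 27% | 73% |
| 15% | 30% | 42% | 58% |
| 20% | 40% | 57% | 43% |
| 25% | 50% | 72% | 28% |
| 30% | 60% | 85% | 15% |

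The chance of printing reaches 50% at an OMT rate of about 17.6%, and 80% at about 27.8%.

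**With the protocol's LCIG rates and OMT at half.**

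| Event | LCIG | OMT (assumed) | P printed | P cell empty |
|---|---|---|---|---|
| Weight decreased | 14.3% | 7.2% | 17.9% | 82% |
| Insomnia | 23.3% | 11.7% | 31.3% | 69% |
| Abdominal pain | 28.2% | 14.1% | 38.8% | 61% |
| Any serious event | 47.1% | 23.6% | 67.6% | 32% |

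Seven of the 25 Table 1 terms are by name device or procedure harms, for which halving makes little sense because OMT subjects receive no tube in the 26 weeks. That leaves 25 - 7 = 18 terms. With OMT at half, all 18 are more likely unprinted than printed: print chance 10% (headache, 10.0%) to 39% (abdominal pain, 28.2%). If the listed rate is instead taken as the OMT rate and LCIG doubles it, 13 of the 18 lie below 17.6% and are still more likely unprinted.

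**Procedure harms with OMT at 0%.** P prints in 96% to 100% of trials for the five terms at 20% to 33%, in 80% at 14.8%, and in 53% at 10.9%.

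**Where the threshold falls in observed counts.** 7/44 vs 14/44 gives P = 0.132, not printed. 8/44 vs 16/44 gives P = 0.093, the first observed doubling to print. 0/44 vs 4/44 gives P = 0.116, not printed; 0/44 vs 5/44 gives P = 0.055, printed.

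**What an interval would add.** Take OMT 4/44 = 9.1% and LCIG 8/44 = 18.2% (P = 0.352, not printed). The 95% Wilson limits are 3.6% to 21.2% and 9.5% to 32.0%. Newcombe's interval for the difference of 9.1 points is:

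- lower: 9.1 - √[(18.2 - 9.5)² + (21.2 - 9.1)²] ≈ -5.8 points
- upper: 9.1 + √[(32.0 - 18.2)² + (9.1 - 3.6)²] ≈ +23.9 points

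**Sensitivity to arm size.** The LCIG safety set requires device placement (SAP 5.0), so it may fall below 44. For 10% vs 20%, the print chance is 27% at 44 vs 44, 30% at 44 (OMT) vs 40 (LCIG), and 22% at 37 vs 37. Fisher's discreteness makes it move unevenly, but the conclusion stays.

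**The case against.** The strongest reply is that this concerns presentation only. Every row shows the number and percentage in each arm, so 9.1% versus 18.2% is in plain view and the difference is a subtraction. SAP 10.2 also plans an overview, severity and relationship tables, special-interest tables, subgroups and listings. The threshold is prespecified and looser than the 0.050 test level. All of this stands, so it would be wrong to say that a doubling shows as a blank: only the P cell is empty, and what is missing is an estimate with its uncertainty.

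Other limits also stand:

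- The suppression rule is not stated for the special-interest tables. Their gap is the missing interval.
- Weight change as a continuous variable already has a between-arm 95% interval (SAP 10.4.1), and weight loss of at least 7% is counted by arm (SAP 10.4.3 and Appendix G).
- Most procedure harms near zero on OMT would be flagged.
- For any serious event, in the scenario above, a printed P value is the likelier outcome.

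A reader might infer that the plan treats an unprinted P value as a finding of no difference. The documents do not support this. Neither states it, sets a decision rule for safety, or plans a conclusion of no excess harm. The risk lies in how such tables may be read.

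**Conclusion.** The point holds in limited form. Fisher's test is the only planned between-arm inference for adverse events, P values above 0.100 are withheld in the SAP 10.2.2 tables, and no interval is planned for any adverse event. At 44 per arm a true doubling leaves the P cell empty more often than not when the OMT rate is below about 18%. In that range the planned tables do not show how large an excess is still compatible with the data; for 4/44 versus 8/44 it is up to about 24 percentage points.

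The size rests on assumed OMT rates and on LCIG rates from a mean exposure of 854 days, against 26 × 7 = 182 days here. Rates in this trial are probably lower, which would make an empty cell more likely. The documents set no acceptable miss rate for safety, so these figures describe the display and do not show that a stated standard is failed. No dataset, sample size or primary conclusion is affected.

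**What to change.** In SAP 10.2.2, delete the P ≤ 0.100 display rule. For any TEAE, any serious TEAE, any TEAE leading to discontinuation and each special-interest composite (GI and procedure, polyneuropathy, weight loss), report the LCIG minus OMT risk difference with a 95% confidence interval, for example by Miettinen–Nurminen. Add a sentence that a non-significant Fisher test will not be read as absence of excess risk.

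The cost is SAP wording and one column in tables already planned, with no new data. The intervals will be visibly wide, which is the information the reader needs.

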6.1.3 Relationship to Study Drug

For the assessment of drug event relationship, LCIG should be considered a therapeutic system consisting of drug, devices and placement procedure. Causality assessments are always made over the system as a whole.

For the assessment of drug event relationship, those randomized to OMT should evaluate relatedness to any of the subject's anti-PD medication.

The Investigator will use the following definitions to assess the relationship of the adverse event to the use of study drug:

Reasonable Possibility	After consideration of factors including timing of the event, biologic plausibility, clinical judgment, and potential alternative causes, there is sufficient evidence (information) to suggest a causal relationship.
No Reasonable Possibility	After consideration of factors including timing of the event, biologic plausibility, clinical judgment, and potential alternative causes, there is insufficient evidence (information) to suggest a causal relationship.

For causality assessments, events assessed as having a reasonable possibility of being related to the study drug will be considered "associated." Events assessed as having no reasonable possibility of being related to study drug will be considered "not associated." In addition, if the Investigator has not reported causality or deemed it not assessable, AbbVie will consider the event associated.

[figure not shown]
If an Investigator's opinion of no reasonable possibility of being related to study drug is given, an Other cause of event must be provided by the Investigator for the serious adverse event.

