8.1.4.2 Adverse Events

Adverse events will be coded using the most current version of the Medical Dictionary for Regulatory Activities (MedDRA). Adverse events will be summarized by primary MedDRA system organ class (SOC) and preferred term (PT). Subjects reporting more than one adverse event for a given MedDRA PT will be counted only once for that term. Subjects reporting more than one adverse event within an SOC will be counted only once for the SOC total. Subjects reporting more than one adverse event will be counted only once in the overall adverse event total.

Each adverse event will be categorized by severity (mild, moderate, severe) and by relationship to study treatment (reasonable possibility, or no reasonable possibility). Detailed search criteria for adverse events of special interest (AESIs) will be defined in a SAP prior to database lock.

A treatment-emergent adverse event (TEAE) is defined as:

- For OMT group: any adverse event that begins or worsens in severity the day after randomization and within 30 days following the last visit.
- For the LCIG group: any adverse event that begins or worsens in severity from the day of the initial device placement (NJ or PEG-J) through Week 26 Visit for those subjects continuing to LCIG commercial treatment, or through 30 days after final device removal for those subjects not continuing LCIG commercial treatment.

A summary of the number and percentage of subjects will be prepared for the following:

- TEAEs
- TE Serious AEs (including deaths)
- TEAEs leading to premature discontinuation of treatment
- TEAEs by maximum relationship to study drug
- TEAEs by maximum severity
- Treatment-emergent AESIs

Serious adverse events with onset during the Screening Period for all subjects screened, adverse events and serious adverse events with onset after day of randomization and before day of initial device placement for the LCIG group, as well as adverse events during the transition period for LCIG subjects continuing LCIG commercial treatment will also be summarized.

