10.2.1 Adverse Event Overview

The number and percentage of subjects experiencing one or more adverse events in the following adverse event categories during the 26-week Treatment Period and during the Extension/Transition Period will be summarized.

- Any TEAE
- Any TEAE that was rated by the investigator as having a reasonable possibility of relationship to levodopa-carbidopa intestinal gel
- Any severe TEAE
- Any serious TEAE
- Any TEAE that led to discontinuation of study drug
- Any treatment emergent GI event (as defined in Section 10.2.3)
- Any TEAE other than a GI event (as defined in Section 10.2.3)
- A fatal TEAE
- All deaths

Serious adverse events with onset during the Screening Period for all subjects screened, adverse events and serious adverse events with onset after day of randomization and before day of initial device placement for the LCIG group, as well as adverse events during the transition period for LCIG subjects continuing LCIG commercial treatment will also be summarized.

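### The SAP tabulates adverse events with missing or non-assessable causality as 'unknown', where the protocol treats them as associated, so related-event counts can fall below the protocol's rule

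*SAP*

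**What the plan says.** **Protocol 6.1.3 (Relationship to Study Drug)** has the investigator choose between two ratings, reasonable possibility and no reasonable possibility. The first makes an event associated and the second makes it not associated. The section then covers the remaining case: "if the Investigator has not reported causality or deemed it not assessable, AbbVie will consider the event associated".

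**Protocol 8.1.4.2 (Adverse Events)** lists the same two relationship categories for analysis and plans a summary by maximum relationship to study drug.

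**SAP 10.2.2 (Adverse Event Incidence)** summarises subjects by "maximum relationship category (reasonable possibility, no reasonable possibility, or unknown), as assessed by the investigator", which is three levels. On the third level it says: "If a subject has an adverse event with unknown relationship, then the subject will be counted in the relationship category of" 'unknown', even if another occurrence of the same event has a rating. The one exception is another occurrence rated as a reasonable possibility, which puts the subject in that category.

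**SAP 10.2.1 (Adverse Event Overview)** has one line on relationship: "Any TEAE that was rated by the investigator as having a reasonable possibility of relationship to levodopa-carbidopa intestinal gel". It has no line for events of unknown relationship.

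**SAP 12.0 (Summary of Changes)** states that the analysis does not differ from the latest protocol version, Amendment 4.

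**The concern.** The protocol resolves a missing causality judgement in the conservative direction. The SAP leaves it unresolved in one table and has no place for it in the other. An event that the sponsor has undertaken to treat as associated could then be absent from the trial's own count of related events, and SAP 12.0 would not alert the reader.

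Safety and tolerability are a secondary objective. Protocol 6.1.3 also has causality judged over drug, devices and placement procedure as one system. The related-event summaries are where a reader would look for the burden attributed to that system, so they should follow the protocol's rule or say openly that they do not.

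**Working it through.** The documents give no number of related events and no number of missing causality ratings, so there is no figure of the plan's to reproduce. The check is on the counting rule.

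**Step 1: one preferred term.** Let R be a rating of reasonable possibility, N no reasonable possibility, and U missing or not assessable. The SAP does not define 'unknown'; reading it as U is an inference, but the natural one. A subject with at least one occurrence of a term has one of seven sets of ratings.

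- SAP 10.2.2 rule: related if the set contains R; otherwise unknown if it contains U; otherwise not related.
- Protocol 6.1.3 rule: related if the set contains R or U; otherwise not related.

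| Ratings for the term | SAP 10.2.2 | Protocol 6.1.3 | Same? |
|---|---|---|---|
| R | related | related | yes |
| N | not related | not related | yes |
| U | unknown | related | **no** |
| R, N | related | related | yes |
| R, U | related | related | yes |
| N, U | unknown | related | **no** |
| R, N, U | related | related | yes |

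Two of the seven sets differ: unknown only, and not related plus unknown. No set is related under the SAP but not under the protocol. For every preferred term, therefore, the SAP related count is at or below the protocol count.

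**Step 2: size in a preferred-term row.** If k subjects in an arm of n fall in the two differing sets, the row is lower by 100 × k / n percentage points. The planned n is 44 per arm (Protocol synopsis). The documents give no k, so these values are assumptions:

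- k = 0: 0
- k = 1: 100 × 1/44 = 2.27
- k = 2: 100 × 2/44 = 4.55
- k = 3: 100 × 3/44 = 6.82
- k = 5: 100 × 5/44 = 11.36

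The safety dataset leaves out LCIG subjects who had no device placed, so n in that arm may be below 44. At n = 40, one subject is 100 × 1/40 = 2.5 points.

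**Step 3: the overview line.** The unit here is a subject across all terms. Under the protocol's rule a subject counts if any event is R or U; under SAP 10.2.1, only if at least one is R. The difference is the number of subjects with at least one U and no R on any term. A subject with one missing rating and any other related event is still counted, so the row-level figures in Step 2 do not carry over to this line.

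**The case against.** **The two rules have different authors.** The protocol sentence says what the sponsor will consider, while both SAP outputs are labelled as the investigator's assessment. SAP 10.2.2 also adds an 'unknown' level to severity, with a similar exception, so this looks like a general display convention for missing data. The argument is fair, and it weakens any inference from the two-level list in Protocol 8.1.4.2 alone. It does not remove the conflict. The sponsor's rule stands in the protocol's general section on causality, and the text available does not limit it to expedited reporting. If an investigator-only display is intended, SAP 12.0 should say so.

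**Nothing is hidden in the table.** A reader might infer that the SAP reverses the protocol. It does not: the unknown category is printed by system organ class and preferred term, and it outranks no reasonable possibility, so these events are not relabelled as unrelated. A reader can add the column back. That holds for the SOC and term table, but not for the overview, where the information cannot be recovered.

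**There may be nothing to count.** Protocol 6.1 requires the investigator to record relationship for every event, Protocol 10.2 has case report forms reviewed for completeness, and Protocol 11.0 adds logic and manual checks. Missing ratings may be few or none. This stands, and it limits the point to what can happen.

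**Most LCIG subjects may have another related event.** Protocol 3.0 reports complication of device insertion in 56.8% and abdominal pain in 51.4% in the pivotal study, and causality covers the procedure. Many LCIG subjects would then stay in the overview count despite a missing rating. This is plausible, although those percentages are not causality ratings.

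**Conclusion.** The inconsistency is real and undeclared. Following the SAP as written can give related-event counts below those of Protocol 6.1.3, and cannot give counts above them. With an assumed 44 per arm, each affected subject is 2.3 points in a single preferred-term row. The overview line changes only for subjects who have an event of unknown causality and no related-rated event at all.

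Two stronger readings are not supported. One is that related counts *are* understated: the documents give no number of missing ratings, and with none the effect is zero. The other is that the overall related-event rate would fall by several points: that needs both an assumed number of missing ratings and the further assumption that those subjects have no other related event.

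Primary efficacy, alpha and sample size are untouched. The point should be settled before database lock because it concerns a stated protocol rule and the repair is small.

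**What to change.** In SAP 10.2.1 and 10.2.2, state that for the related-event summaries a causality rating that is missing or not assessable counts as a reasonable possibility. Show the number so assigned in each arm as a footnoted subset, so that genuine investigator ratings and missing data both stay visible and the sponsor's default is not presented as an investigator's judgement. Define in the same place what 'unknown' covers.

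If the sponsor prefers to keep a separate 'unknown' column, it should add a matching row to the overview and declare and justify the departure in SAP 12.0.

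The cost is about two sentences and one derivation. The downside is that related counts may become slightly less favourable.
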